**Figure 11-1 Operating characteristics for the planned interim and final analyses**

[figure not shown]

Figure 11-1 shows the operating characteristics curves for the planned interim and final analyses. The horizontal axis shows the difference CFZ533 minus placebo in mean QMG change from baseline (from 0 to 6). The vertical axis displays the probabilities (i) success (target efficacy, green curves), (ii) futility (red curves), and (iii) indeterminate (neither success nor futility achieved (yellow curves)).

### 11.7 Power for analysis of key secondary variables

MGC score is a key secondary variable. It ranges from 0 to 53, with a SD of 6.6. The change from baseline is assumed to be normally distributed. With 36 patients, the study will have more than 80% power to detect a difference of 4.7 between CFZ533 and placebo mean change from baseline using a 1-sided t-test at 10% significance level.

## **12 Ethical considerations**

### **12.1 Regulatory and ethical compliance**

This clinical study was designed and shall be implemented and reported in accordance with the ICH Harmonized Tripartite Guidelines for Good Clinical Practice, with applicable local regulations (including European Directive 2001/20/EC, US Code of Federal Regulations Title 21, and Japanese Ministry of Health, Labor, and Welfare), and with the ethical principles laid down in the Declaration of Helsinki.

### **12.2 Responsibilities of the investigator and IRB/IEC**

Before initiating a trial, the investigator/institution should obtain approval/favorable opinion from the Institutional Review Board/Independent Ethics Committee (IRB/IEC) for the trial protocol, written informed consent form, consent form updates, subject recruitment procedures (e.g. advertisements) and any other written information to be provided to subjects. Prior to study start, the investigator is required to sign a protocol signature page confirming his/her agreement to conduct the study in accordance with these documents and all of the instructions and procedures found in this protocol and to give access to all relevant data and records to Novartis monitors, auditors, Novartis Quality Assurance representatives, designated

agents of Novartis, IRBs/IECs, and regulatory authorities as required. If an inspection of the clinical site is requested by a regulatory authority, the investigator must inform Novartis immediately that this request has been made.

For multi-center trials, a Coordinating Investigator will be selected by Novartis around the time of Last Patient Last Visit to be a reviewer and signatory for the clinical study report.

### **12.3 Publication of study protocol and results**

Novartis assures that the key design elements of this protocol will be posted in a publicly accessible database such as [clinicaltrials.gov](http://clinicaltrials.gov). In addition, upon study completion and finalization of the study report the results of this trial will be either submitted for publication and/or posted in a publicly accessible database of clinical trial results.

## **13 Protocol adherence**

This protocol defines the study objectives, the study procedures and the data to be collected on study participants. Additional assessments required to ensure safety of subjects should be administered as deemed necessary on a case by case basis. Under no circumstances should an investigator collect additional data or conduct any additional procedures for any research related purpose involving any investigational drugs.

Investigators must apply due diligence to avoid protocol deviations. If the investigator feels a protocol deviation would improve the conduct of the study this must be considered a protocol amendment, and unless such an amendment is agreed upon by Novartis and approved by the IRB/IEC/REB it cannot be implemented. All significant protocol deviations will be recorded and reported in the CSR.

### **13.1 Protocol Amendments**

Any change or addition to the protocol can only be made in a written protocol amendment that must be approved by Novartis, Health Authorities where required, and the IRB/IEC prior to implementation.

Only amendments that are intended to eliminate an apparent immediate hazard to subjects may be implemented, provided the Health Authorities and the reviewing IRB/IEC are subsequently notified by protocol amendment.

Notwithstanding the need for approval of formal protocol amendments, the investigator is expected to take any immediate action required for the safety of any subject included in this study, even if this action represents a deviation from the protocol. In such cases, the CTL should be informed and (serious) adverse event reporting requirements ([Section 9](#)) followed as appropriate.

1.1 Scope

The RAP documents contain detailed information to aid the production of Statistics & Programming input into the Clinical Study Report (CSR) for trial “**CCFZ533X2204**”.

Module 3 (M3) provides the description of the statistical methodology used to analyze the data, **Module 7 (M7)** details the presentation of the data, including shells of summary tables, figures and listings, and **Module 8 (M8)** contains programming specifications e.g. for derived variables and derived datasets, to support the creation of CSR outputs.

1.2 Changes to RAP documentation (M3)

Refer to corresponding guidances and NIBR RAP Addendum template for detailed information on the requirements of documenting changes to RAP documentation.

For the statistical methodology (M3), any major changes to the statistical methodology should be reflected in the RAP M3 documentation via version control (M3 amendment) (new document version to be approved by the trial team as the original module).

Such major changes could include (but are not limited to):

- change in statistical methodology
- substantial change in (derivation of) main endpoint
- substantial change in study design (e.g. protocol amendment introducing new multiple-dose cohorts in a so far single-dose trial)

Such changes may also require a protocol amendment to ensure consistency. In addition they need to be mentioned (high-level) in the CSR (section for changes to planned analysis).

Minor changes to the RAP M3 documentation can be captured e.g. by a study note to file / note in RAP Addendum or within the CSR itself. Corporate Confidential Information

Corrections of typographical errors or modification of spelling (from English to American, for example) do not need to be incorporated into the RAP M3 documentation.

Analyses and outputs related to additional exploratory ad-hoc requests used for reporting are regarded minor changes and should be documented in the RAP addendum (no RAP amendment necessary).

2 Study objectives and design

2.1 Study objectives

2.1.1 Primary objectives

- To evaluate the safety and tolerability of IV CFZ533 as an add-on therapy to standard of care in patients with moderate to severe Myasthenia gravis (MG) throughout the study
- To evaluate the efficacy of IV CFZ533 as an add-on therapy to standard of care in patients with moderate to severe MG

2.1.2 Secondary objectives

- To evaluate the efficacy of IV CFZ533 using relevant MG related outcome measures throughout the 24 weeks treatment period
- To evaluate the decay in efficacy of IV CFZ533 using relevant MG related outcome measures throughout the 24 weeks follow-up period
- To evaluate changes in patient's quality of life (QOL) throughout the 24 weeks treatment period
- To evaluate the PK of 2-hour IV infusion of CFZ533 at 10 mg/kg administered q4w for 6 doses (endpoint: free CFZ533 in plasma)
- To evaluate the PD of CFZ533 (CD40 saturation on B cells, extent/duration of target engagement (endpoints: free CD40 on B cells, total CD40 on B cells, and total soluble CD40 in plasma)
- To assess immunogenicity in CFZ533-treated patients and in placebo-treated patients (pre-existing anti-drug antibodies)

Corporate Confidential Information

2.2 Study design and treatment

This is a randomized double-blind, placebo controlled, non-confirmatory study to preliminarily evaluate the safety, tolerability, PK/PD, and efficacy of IV CFZ533 administered every four weeks (q4w) over a 24 week treatment period in patients with moderate to severe MG. The investigational drug or placebo will be administered in addition to standard of care therapy for MG.

[figure not shown]
Patients should remain on their standard of care therapies and the dose should be maintained at a constant level during the study. For patients that are receiving corticosteroids at baseline, a predefined steroid tapering will be allowed after achievement of minimal manifestations (MM) state (Jaretzki et al 2000).

Patients on cholinesterase inhibitors (CI) should remain on stable doses throughout the study, but CIs should not be taken for at least 12 hours prior to QMG and MG composite testing at each visit, in order to reduce fluctuations in performance on functional tests due to the temporary symptomatic effects associated with CI use.

For each patient, there will be two screening visits. Most of the screening assessments are done during Screening Visit 1 (Day -28 to Day -8), while Screening Visit 2 (Day -7 to Day -3) is performed to collect a blood sample to allow laboratory results (chemistry, hematology, and pregnancy test, if applicable) to be available prior to randomization on Day 1. All laboratory results must be available prior to dosing (Day 1-Visit 3) and meet eligibility criteria. Once continued eligibility is confirmed, patients will be assigned a randomization number at Day 1 and receive CFZ533 or placebo via a 2-hour intravenous infusion. Patients will be dosed every four weeks (q4w) according to their randomization for a total of 6 doses on Day 1 ± 2 (Week 1), Day 29 ± 2 (Week 5), Day 57 ± 2 (Week 9), Day 85 ± 2 (Week 13), Day 113 ± 2 (Week 17) and Day 141 ± 2 (Week 21). The treatment period (24 weeks) will be followed by a safety follow-up period of other 24 weeks. The duration of the entire study including screening will be approximately 52 weeks.

An overview of the study design is given in Figure 2-1.

Figure 2-1 Study design

3 First interpretable results (FIR)

First interpretable results (FIR) will be provided for this trial.

The study FIR template (mock slides) can be found in CREDI in the study RAP folder.

The template shows the analysis / results to be presented in the FIR. Study outputs required to be created at the time of the FIR will be highlighted in RAP Module 7 and marked as “Key” in the M9.1 Tracking sheet output list.

Corporate Confidential Information

5 Statistical methods: Analysis sets

For subjects for which the actual treatment received does not match the randomized treatment the treatment actually received will be used for the analysis.

The full analysis set (FAS) will include all patients who received any study drug.

The safety analysis set will include patients who received any study drug.

The PD analysis set will include all patients who received any study drug and with no protocol deviations with relevant impact on efficacy data.

The PK analysis set will include patients with available PK data and no protocol deviations with relevant impact on PK data.

The analysis sets and protocol deviation codes are related as follows:

Table 5-1 Protocol deviation codes and analysis sets

Category Deviation code	Text description of deviation	Data exclusion	
Subjects are excluded from all (safety) analysis in case of these PDs:		Exclude subject completely from all (safety) analysis sets	
I##	ICF not obtained		
I##	ICF was signed after the other screening procedure; ICF wrong version was obtained.		
E##	xxxxxxx		
Subjects are excluded from PK analysis in case of these PDs:		Exclude subject from PK analysis set	
I06	Deviation from inclusion criterion 6.		YES
E##	xxxxxxx		

Category Deviation code	Text description of deviation	Data exclusion
Subjects are excluded from PD analysis in case of these PDs:		Exclude subject from PD analysis set
I06	Deviation from inclusion criterion 6.	YES
E##	xxxxxxx	
Subjects are excluded from PK and PD analysis in case of these PDs:		Exclude subject from PK and PD analysis sets
I06	Deviation from inclusion criterion 6.	YES
E##	xxxxxxx	
Subjects are excluded from PD analysis at the impacted visit in case of these PDs:		Exclude subject from PD analysis set at the impacted visit
M02	Use of Cholinesterase inhibitors less than 12 hours prior to QMG and MGC testing.	YES

If updates to this table are needed, an amendment to RAP M3 needs to be implemented prior to DBL.

6 Statistical methods for Pharmacokinetic (PK) parameters

6.1.1 Variables

The following PK parameters will be determined, if data permit, using the actual recorded sampling times and non-compartmental method(s) with Phoenix WinNonlin (Version 6.2 or higher): C_{max}, C_{max,ss}, C_{min,ss}, T_{max}, AUC_{tau}, AUC_{tau,ss} and C_{av,ss} from the plasma concentration-time data.

In the zz.xpt file in GPSII (merge file), PK concentration (free CFZ533 in plasma) will be expressed in unit 'microg/mL' (in addition to 'nanog/mL'), and time will be expressed in unit 'day' (in addition to 'hours'). Two variables for the elapsed time will be provided: (i) elapsed time since first dose, and (ii) elapsed time since last dose.

Corporate Confidential Information

6.1.3 Statistical model, assumptions and hypotheses

Not applicable.

6.1.4 Model checking procedures

Not applicable.

6.1.5 Graphical presentation of results

Arithmetic mean (SD) and geometric mean (95% CI) plasma concentration data will be plotted across time.

Overlaying individual plasma concentration-time profiles will be generated.

Corporate Confidential Information

7 Statistical methods for Pharmacodynamic (PD) parameters

7.1 Primary objective

The primary objectives of this study are to preliminarily evaluate the safety, tolerability and efficacy of IV CFZ533 in moderate to severe Myasthenia Gravis patients after 24 weeks of treatment as an add-on therapy to standard of care as compared to placebo.

7.1.1 Variables

The primary efficacy variable is the change from baseline in QMG score after 24 weeks of treatment (at Week 25 visit). The baseline value will be the predose assessment on Day 1. It is assumed that the change from baseline in QMG score is normally distributed.

The analysis of safety and tolerability is descriptive and detailed below in Section 8.

7.1.2 Descriptive analyses

Descriptive summary statistics will be provided by treatment and visit/sampling time point. Summary statistics will include mean, SD, median, minimum and maximum.

7.1.4 Graphical presentation of results

Arithmetic mean (\pm SD) of QMG score and change from baseline in QMG score will be plotted across time.

The posterior probability distribution from the Bayesian analysis will be plotted at Week 25.

7.1.5 Handling of missing values/censoring/discontinuations

No imputation of missing data dropouts or any other reason will be done. The main analysis model will include all data of all patients in the PD analysis set, including dropouts.

7.2 Secondary objectives

7.2.1 Variables

Secondary efficacy/pharmacodynamic variables include:

- change from baseline in MGC score after 24 weeks of treatment (at Week 25 visit)
- proportion of patients requiring rescue therapy (i.e. IV immunoglobulins or plasma exchange).
- mean change from baseline in QMG Score and MGC Score at all visits
- proportion of patients with improvement by ≥ 3 points in QMG score
- proportion of patients with worsening by ≥ 3 points in QMG score
- proportion of patients intolerant to steroid taper (i.e the proportion of patients that will require to reinstitute their previous steroid dose)
- proportion of patients who discontinued due to inefficacy or worsening
- Mean change in the Myasthenia Gravis Activities of Daily Living Scales (MG-ADL, MG QOL-15).
- Free and total CD40 on B cells (peripheral blood)
- Total soluble CD40 in plasma.

The baseline value for all secondary variables will be the predose assessment on Day 1.

An improvement is a reduction in QMG score and worsening is an increase in QMG score.

7.2.2 Descriptive analyses

Descriptive summary statistics of efficacy data will be provided by treatment and visit/sampling time point. Summary statistics will include mean, SD, median, minimum and maximum.

7.2.3 Statistical model, assumptions and hypotheses

The changes from baseline in MGC scores at each visit of the treatment period (weeks 5, 9, 13, 17, 21 and 25) will be analyzed using a mixed effect model for repeated measurements. The model may investigate effects for treatment (CFZ533 or placebo), time (visit week), baseline MGC score, treatment by time and baseline by time interactions. An unstructured covariance matrix may be used to model the correlations between the measurements in the same subject. In case of convergence issues, the covariance matrix that best fit the data will be chosen. The estimated treatment differences at each visit will be provided with 90% CI and 2-sided p-values.

Other potentially influential factors such as sex, age at onset of the disease, markers of baseline severity of the disease or prednisone dose may be explored.

The changes from baseline in MG-ADL and MG QOL-15 at each visit until Week 25 will be analyzed using the main mixed model as described above for MGC.

The proportions of patients requiring rescue therapy between Week 1 and Week 25 (i.e. IV immunoglobulins or plasma exchange) will be summarized. Time to first rescue therapy will be described using Kaplan-Meier curves and compared between CFZ533 and placebo using the logrank test. In case of dropouts, the data will be censored at the last visit before or at Week 25.

The changes from baseline in MGC score at Week 25 will be analyzed using the Bayesian model described above.

The proportion of patients with improvement by ≥ 3 points in QMG score at Week 25, the proportion of patients with worsening by ≥ 3 points in QMG score at Week 25, the proportion of patients intolerant to steroid taper and the proportion of patients who discontinued due to inefficacy or worsening before Week 25 will be analyzed via logistic regression with treatment as a factor (and baseline value as a covariate if relevant) compared between CFZ533 and placebo. Additional covariates such as sex, gender, age at onset of MG, QMG score at baseline will be explored. Odds ratios together with 90% CI and p-values will be provided for comparisons of CFZ533 versus placebo utilizing the logistic regression model fitted.

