### **11.4.4 Supportive analyses**

In order to assess the robustness of the results, the primary analysis will be repeated on the FAS.

In addition, the changes from baseline in QMG scores at each visit of the treatment period (weeks 5, 9, 13, 17, 21 and 25) will be analyzed using a mixed effect model for repeated measurements. The model may investigate effects for treatment (CFZ533 or placebo), time (visit week), baseline QMG score, treatment by time and baseline by time interactions. An unstructured covariance matrix may be used to model the correlations between the measurements in the same subject. In case of convergence issues, the covariance matrix that best fit the data will be chosen. The estimated treatment differences at each visit will be provided with 90% CI and 2-sided p-values.

Other potentially influent factors such as sex, age at onset of the disease, makers of baseline severity of the disease or prednisone dose may be explored.

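### Decay of efficacy over follow-up is a secondary objective, but the visible longitudinal models stop at Week 25 and leave it only raw means, which can mislead in either direction

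*SAP*

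**What the plan says.** SAP 2.1.2 states the objective: "To evaluate the decay in efficacy of IV CFZ533 using relevant MG related outcome measures throughout the 24 weeks follow-up period". Protocol 2.2 carries the same objective; its endpoint cell reads as empty in the available text, which may be a table-extraction effect. SAP 2.2 gives the length of the period: "The treatment period (24 weeks) will be followed by a safety follow-up period of other 24 weeks".

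The visible longitudinal analyses end earlier:

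- **MGC** (SAP 7.2.3): "The changes from baseline in MGC scores at each visit of the treatment period (weeks 5, 9, 13, 17, 21 and 25", in a mixed model for repeated measures.
- **QMG** (Protocol 11.4.4, supportive model): "the changes from baseline in QMG scores at each visit of the treatment period (weeks 5, 9, 13, 17, 21 and 25".
- **Quality of life** (SAP 7.2.3): "The changes from baseline in MG-ADL and MG QOL-15 at each visit until Week 25".
- **Rescue** (SAP 7.2.3): "The proportions of patients requiring rescue therapy between Week 1 and Week 25", with time to rescue censored at or before Week 25.
- **QMG improvement and worsening** are analysed at Week 25, and discontinuation for inefficacy or worsening before Week 25.

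What reaches the follow-up period is the variable "mean change from baseline in QMG Score and MGC Score at all visits" (SAP 7.2.1), measured from the Day 1 predose value. SAP 7.2.2 says how it is treated: "Descriptive summary statistics of efficacy data will be provided by treatment and visit/sampling time point", meaning mean, SD, median, minimum and maximum. SAP 7.1.4 and 7.2.5 add plots of means over time. SAP 7.1.5 plans no imputation.

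Protocol Table 6-1 lets steroid dosing after Week 25 follow need and usual standard of care. Protocol 6.9 lets rescued patients stay in the study.

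**The concern.** Decay is a contrast: how far the CFZ533–placebo difference at Week 25 has shrunk by a later visit, or how far the CFZ533 arm has moved from its own Week 25 level. SAP 7.2 defines neither. The reader would have to subtract one raw mean from another.

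That subtraction has three weaknesses. The two means come from different patients if anyone leaves after Week 25. No interval goes with it. And the scores may be taken after a steroid increase (in patients receiving corticosteroids) or after rescue, with no stated rule for either and no planned summary of rescue after Week 25. Persistence of effect after the last dose is what the objective asks about, and the study is meant to supply preliminary data for further development.

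**Working it through.** **1. The plan's own figures.** The documents give no figure for decay. The nearest is the MGC power in Protocol 11.7 (36 patients, difference 4.7, SD 6.6, one-sided 10%). SE = 6.6 × √(2/18) = 2.2; 4.7/2.2 = 2.136; 2.136 − 1.282 = 0.855, so power is 80.4%. The exact t calculation gives 79.6%. The stated figure, more than 80%, is reproduced to within rounding of method. Expected loss over the whole study is (44 − 36)/44 = 18% (Protocol 4), described as about 20% in Protocol 11.6.

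**2. Effect of leaving on raw means.**

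From the documents: 22 patients per arm and SD 5.5 (Protocol 11.6). Assumed: within-patient correlation 0.7 between Week 25 and follow-up; CFZ533 3.0 points better at Week 25 with all of it lost by follow-up; placebo flat; the same logistic leaving rule in both arms, driven by Week 25 QMG (slope 1.2 per SD). The true loss is then 3.0 on both contrasts.

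- Raw decline in an arm = follow-up mean of those remaining − Week 25 mean of all.
- Raw lost arm difference = raw decline on CFZ533 − raw decline on placebo.

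| Leaving CFZ533 / placebo | Raw decline, CFZ533 | Raw lost arm difference | Conditioning on Week 25, both contrasts |
|---|---|---|---|
| about 11% / 18% | 2.55 | 3.26 | about 3.0 |
| about 22% / 32% | 2.16 | 3.34 | about 3.0 |
| about 31% / 43% | 1.85 | 3.46 | about 3.0 |

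The within-arm decline is understated because the worse patients leave. The lost arm difference is overstated because placebo patients are worse at Week 25, so more of them leave and the remaining placebo mean looks better. Tabulating change from Week 25 among stayers does not cure this: within CFZ533 it gave 3.19, 3.34 and 3.50 at 11%, 22% and 32% leaving.

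**3. Scale against the plan.** Even the first row means 22 × 0.11 + 22 × 0.18 = 6.4 patients leaving after Week 25, against 8 expected to leave over the whole study. The other two rows exceed the plan's total. In the first row the within-arm bias is 3.0 − 2.55 = 0.45 points. The SE of one arm's mean change is 5.5 × √(2 × 0.3) / √22 = 0.91. The bias in the arm difference is 0.26, against an SE of 0.91 × √2 = 1.28.

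**4. Leaving or re-treatment by arm.** Different assumptions: correlation 0.6; true lost arm difference 4.5; a worsener gains 3 or more points after Week 25; extra steroid improves QMG by 2 points. Observed lost arm difference:

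| Scenario | Both arms | CFZ533 only | Placebo only |
|---|---|---|---|
| 40% of worseners leave | 4.4 | 4.0 | 4.9 |
| 50% of worseners get extra steroid | 4.15 | 3.9 | 4.8 |

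The error runs from about −0.6 to +0.4 points.

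**5. Precision.** The SE of a raw arm difference at one visit with 18 per arm is 5.5 × √(2/18) = 1.83. The 90% half-width is 1.69 × 1.83 = 3.1 points, rising to 3.4 at 15 per arm and 3.9 at 12. Only a large change could be shown, and the plan gives no interval to make that visible.

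**The case against.** This is a non-confirmatory Phase IIa study and the period is labelled safety follow-up, so means by arm and visit with plots are a defensible preliminary description. The simulated bias is small beside the sampling error at the dropout the plan expects. The correlation, the leaving rule and the steroid effect are not in the documents. The model's near-exact answer is partly built in, because leaving was made to depend only on the score it conditions on. All of this stands, and it limits the point to an improvement.

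Three stronger readings are tempting and not supported:

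- **That loss of effect will be understated, so the drug will look longer-lasting than it is.** This holds for the decline within CFZ533 when worse patients leave or are re-treated. The lost arm difference can move the other way, as the working shows.
- **That no model in the plan looks beyond Week 25.** The primary model sections (Protocol 11.4.2, SAP 7.1.3) and other blocks are withheld, and the steroid-taper regression has no stated window. Only the visible longitudinal models can be described.
- **That steroid dosing is unrestricted in follow-up.** The Table 6-1 entry applies only to patients receiving corticosteroids and refers to usual standard of care.

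Nor does rescue imply leaving. Rescued patients may remain, so their later scores can enter the means.

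**Conclusion.** The point holds as a cheap improvement. A stated secondary objective has, in the visible text, no defined contrast, no arm difference and no interval. The raw means left to answer it are open to bias of either sign: about 0.45 points too low within CFZ533 and about 0.26 too high for the lost arm difference, for a true loss of 3.0 with about 11% and 18% leaving. These sizes rest on the assumed SD, correlation and leaving rule. Re-treatment after Week 25 can add to or offset them, depending on the arm. The direction in the actual trial cannot be predicted from the documents, so the follow-up means should not be read as the drug's decay. The primary Week 25 comparison is unaffected.

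**What to change.** In SAP 7.2.3:

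- Extend the repeated-measures model for QMG and MGC to the scheduled follow-up visits, keeping all Week 5 to Week 25 data in the model so that leaving related to earlier scores is conditioned on.
- Report with 90% confidence intervals the CFZ533–placebo difference at each follow-up visit, its change from Week 25, and the change from Week 25 within each arm.
- Tabulate steroid dose changes and rescue use by arm through follow-up.
- Rerun without scores taken after a steroid increase or rescue as a sensitivity analysis only. Dropping those scores removes patients who are losing effect and so brings its own selection.

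Separately, reconcile the statement in SAP 2.2 and Protocol 3.1 that standard-of-care doses stay constant during the study with the after-Week-25 column of Protocol Table 6-1.

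The cost is SAP wording and a few more model runs. The assessment schedule (Protocol Table 8-1) is not in the available text, so which follow-up visits collect QMG and MGC must be confirmed first. Intervals will be wide at late visits, and the result relies on data being missing at random given the observed scores. With k follow-up visits added, an unstructured covariance grows from 6 × 7/2 = 21 parameters to (6 + k)(7 + k)/2, so the SAP's existing fallback for convergence problems may be needed.
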